**On Day 1 of Cycles 2, 3 and 4, the following procedures will be completed prior to protocol-indicated treatment:**

- Physical Exam.
- Weight
- Vital Signs: Heart rate (HR), blood pressure (BP), and temperature.
- ECOG performance status.
- Concomitant medication and Adverse Event review.
- Complete Blood Count (CBC) with differential (including white blood cell count with differential, hemoglobin, hematocrit, and platelet count).
- Blood Chemistry [including sodium, potassium, chloride, bicarbonate or carbon dioxide, blood urea nitrogen (BUN), creatinine, glucose, total bilirubin, AST, ALT, alkaline phosphatase (ALP), calcium, albumin, total protein; magnesium and phosphorus].
- Additional labs: LDH and TSH (and if TSH is abnormal, then free T3 and free T4). If clinically indicated: ACTH, amylase and lipase.
- **On Cycle 2, Day 1:** Cortisol, troponin-I, CK, and CK-MB.
- **On Cycle 3, Day 1:** Peripheral blood sample for correlative research, and Fresh tumor biopsy ( $\pm 7$  days).

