## 7.2. Study Calendar: Treatment Arm A

Tests and Procedures	Protocol Section	TREATMENT: ARM A: MHC-II (+)		Comments: Arm A All Cycles = 28 days (4 weeks) per cycle	
		4 week cycles			
		CYCLES 1+	CYCLES 1 & 2		
		Day 1 (+1-3d) 	Day 15		
Physical exam, weight 	8.4	X			
Vital Signs 	8.3	X		Heart rate, blood pressure and temperature (oral or tympanic).	
ECOG perform. status 	A2	X			
Review AEs 	8.5 & 11	X		Dose Holds: Section 11. AE reporting: Section 13.	
Review con meds 	8.5 & 10.2	X		Prohibited medications: Section 10.2.	
Hematology 	8.6	X		CBC w/ Diff.	
Serum chemistries 	8.7	X		CMP; Mg, Phos.	
Additional Labs 	8.8	X		LDH, TSH + reflexive (free T3 & free T4), cortisol, CK, and CK-MB.	
		X		If clinically indicated: ACTH, amylase and lipase.	
		c1d1 & c2d1	c1d15 & c2d15	Troponin-I	
Pregnancy test 	8.10	c1d1		Serum or urine (in WOCBP) ≤72hr prior to start of c1d1 tx. Contraception per Appendix 4.	
12-lead ECG 	8.9	c1d1 & c2d1	c1d15 & c2d15	Single tracing on local machine.	
CT or MRI 	8.11	q12 weeks (-1 to -7d) s/p c1d1		Re-scanning every 12 weeks (-1 to -7 days) after initiation of treatment on Cycle 1, Day 1.	
Fresh Tumor Biopsy	8.13		c2d15 (±7d)	(i.e. 6wk s/p c1d1)	
Peripheral blood sample 	8.14	c1d1, c4d1, & c14d1	c1d15 & c2d15	For correlative research. Kits required for collection. (Note: c4d1 & c14d1 are s/p 13 & 53 weeks after c1d1 Arm A tx.)	
TREATMENT: ARM A					
Nivolumab 	9.3	X		30min i.v. infusion: 480mg q4wk (on d1 of Cycles 1+).	
Relatlimab 	9.4	X		60min i.v. infusion: 160mg q4wk (on d1 of Cycles 1+). Relatlimab infusion started AFTER completion of nivolumab infusion.	

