### 7.3. Study Calendar: Treatment Arm B

Tests and Procedures	Protocol Section	TREATMENT: ARM B: MHC-II (-)						Comments: Arm B Cycles 1-4 = 21 days (3 weeks) per cycle Cycles 5+ = 28 days (4 weeks) per cycle	
		3 week cycles			4 week cycles				
		CYCLE 1		CYCLES 2, 3 & 4		CYCLES 5+			
		Day 1	Day 8	Day 15	Day 1 (+1-3d) 	Day 1 (+1-3d) 	Day 1 (+1-3d) 		
Physical exam, Weight 	8.4	X	X	X	X	X			
Vital Signs 	8.3	X	X	X	X	X		Heart rate, blood pressure and temperature (oral or tympanic).	
ECOG perform. status 	A2	X	X	X	X	X			
Review AEs 	8.5 & 11	X	X	X	X	X		Dose Holds: Section 11 . AE reporting: Section 13 .	
Review con meds 	8.5 & 10.2	X	X	X	X	X		Prohibited medications: Section 10.2 .	
Hematology 	8.6	X	X	X	X	X		CBC w/ Diff.	
Serum chemistries 	8.7	X	X	X	X	X		CMP; Mg, Phos.	
Additional Labs 	8.8	X	X	X	X	X		LDH, TSH + reflexive (free T3 & free T4). If clinically indicated: ACTH, amylase and lipase.	
		X	X	X	c2d1			Cortisol, troponin-I, CK, CK-MB.	
Pregnancy test 	8.10	X						Serum or urine (in WOCBP) ≤72hr prior to start of c1d1 tx. Contraception per Appendix 4 .	
CT or MRI 	8.11				q12 weeks (-1 to -7d) s/p c1d1			Re-scanning every 12 weeks (-1 to -7 days) after initiation of treatment on Cycle 1, Day 1.	
Fresh Tumor Biopsy	8.13				c3d1 ±7 days			(i.e. 6wk s/p c1d1)	
Peripheral blood sample 	8.14	X		X	c3d1	c5d1 & c15d1		For correlative research. Kits required for collection. (Note: c5d1 & c15d1 are s/p 13 and 53 Weeks of Arm B tx.)	
TREATMENT: ARM B									
Nivolumab 	9.3	X			X	X		30min i.v. infusion: 1mg/kg q3wk (on d1 of Cycles 1-4), then 480mg q4wk (on d1 of Cycles 5+).	
Ipilimumab 	9.5	X			X			90min i.v. infusion: 3mg/kg q3wk (on d1 of Cycles 1-4). Ipilimumab infusion started AFTER completion of nivolumab infusion.	

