**On Cycles 2+, Day 1, the following procedures will be completed prior to protocol-indicated treatment:**

- Physical Exam.
- Weight
- Vital Signs: Heart rate (HR), blood pressure (BP), and temperature.
- ECOG performance status.
- Concomitant medication and Adverse Event review.
- Complete Blood Count (CBC) with differential (including white blood cell count with differential, hemoglobin, hematocrit, and platelet count).
- Blood Chemistry [including sodium, potassium, chloride, bicarbonate or carbon dioxide, blood urea nitrogen (BUN), creatinine, glucose, total bilirubin, AST, ALT, alkaline phosphatase (ALP), calcium, albumin, total protein; magnesium and phosphorus].
- Additional labs: LDH, TSH (and if TSH is abnormal, then free T3 and free T4), cortisol, CK, and CK-MB. If clinically indicated: ACTH, amylase and lipase.

---

**On the days indicated below, the following additional items will be also be completed (prior to any protocol-indicated treatment):**

- Cycle 2, Day 1:
  - Troponin-I.
  - 12-lead ECG (single recording on local equipment), with additional ECGs as clinically indicated, per patient's study physician.
- Cycle 4, Day 1:
  - Peripheral blood sample for correlative research.
- Cycle 14, Day 1:
  - Peripheral blood sample for correlative research.

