### **7.11. Assessments, Arm B: Cycle 1, Day 8 and Day 15**

**On Cycle 1, Day 8 and Day 15, the following procedures will be completed:**

- Physical Exam.
- Weight
- Vital Signs: Heart rate (HR), blood pressure (BP), and temperature.
- ECOG performance status.
- Concomitant medication and Adverse Event review.
- Complete Blood Count (CBC) with differential (including white blood cell count with differential, hemoglobin, hematocrit, and platelet count).
- Blood Chemistry [including sodium, potassium, chloride, bicarbonate or carbon dioxide, blood urea nitrogen (BUN), creatinine, glucose, total bilirubin, AST, ALT, alkaline phosphatase (ALP), calcium, albumin, total protein; magnesium and phosphorus].
- Additional labs: LDH, TSH (and if TSH is abnormal, then free T3 and free T4), cortisol, troponin-I, CK, and CK-MB. If clinically indicated: ACTH, amylase and lipase.

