### **7.13. Assessments, Arm B: Cycles 5+, Day 1**

**On Cycles 5+, Day 1, the following procedures will be completed prior to protocol-indicated treatment:**

- Physical Exam.
- Weight
- Vital Signs: Heart rate (HR), blood pressure (BP), and temperature.
- ECOG performance status.
- Concomitant medication and Adverse Event review.
- Complete Blood Count (CBC) with differential (including white blood cell count with differential, hemoglobin, hematocrit, and platelet count).
- Blood Chemistry [including sodium, potassium, chloride, bicarbonate or carbon dioxide, blood urea nitrogen (BUN), creatinine, glucose, total bilirubin, AST, ALT, alkaline phosphatase (ALP), calcium, albumin, total protein; magnesium and phosphorus].
- Additional labs: LDH and TSH (and if TSH is abnormal, then free T3 and free T4). If clinically indicated: ACTH, amylase and lipase.
- **On Cycle 5, Day 1:** Peripheral blood sample for correlative research.
- **On Cycle 15, Day 1:** Peripheral blood sample for correlative research.

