### **7.15. End-of-Treatment / Withdrawal Assessments**

Reasonable effort should be made to complete End-of-Treatment (EOT) / Withdrawal procedures on the day it is decided that a patient will no longer receive protocol-indicated treatment.

The following EOT procedures must be completed subsequent to and not later than 14 days after study physician decision to permanently discontinue protocol-indicated treatment with nivolumab, relatlimab or ipilimumab (whichever treatment occurs last) and prior to any subsequent anti-cancer therapy:

- Physical Exam.
- Vital Signs: Heart rate (HR), blood pressure (BP), and temperature.
- ECOG Performance Status.
- Weight.
- Concomitant medication and Adverse Event review.
- Complete Blood Count (CBC) with differential (including white blood cell count with differential, hemoglobin, hematocrit, and platelet count).
- Blood Chemistry [including sodium, potassium, chloride, bicarbonate or carbon dioxide, blood urea nitrogen (BUN), creatinine, glucose, total bilirubin, AST, ALT, alkaline phosphatase (ALP), calcium, albumin, total protein; magnesium and phosphorus].
- Additional labs: LDH and TSH; and, if TSH is abnormal, then also free T3 and free T4.
- Serum or urine Pregnancy Test in women of childbearing potential (as defined in [Appendix 4](#)).
- Disease evaluation by CT/MRI (only if the previous CT/MRI was done > 28 days before).
- Biomarker and pharmacodynamic (PD) blood samples.

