### **8.8. Additional Labs**

Blood draws for additional local laboratory assessment of LDH, TSH, free T3, free T4, cortisol, troponin-I, CK, and CK-MB at time points indicated in [Section 7](#). Designation of “reflexive” in Section 7 indicates assessment of free T3 and free T4 only when TSH is not within normal range. ACTH, amylase and lipase done as clinically indicated per judgment of the investigator.

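### Arm B's scheduled cortisol ends with the pre-dose draw at Cycle 2, Day 1, so none follows ipilimumab doses 2, 3 or 4

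*Combined protocol and SAP*

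**What the plan says.** Both arms have cortisol and ACTH at screening (Sections 7.1 and 7.5).

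In Arm B, the Section 7.3 calendar has one row for "Cortisol, troponin-I, CK, CK-MB". It is marked for Cycle 1 Days 1, 8 and 15 and for Cycle 2 Day 1, and is empty after that. The visit text agrees:

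- Section 7.10 includes cortisol at Cycle 1, Day 1.
- Section 7.11 has, for Days 8 and 15, "cortisol, troponin-I, CK, and CK-MB. If clinically indicated: ACTH, amylase and lipase".
- Section 7.12 gives "Cortisol, troponin-I, CK, and CK-MB" for Cycle 2, Day 1 alone, in a list to be completed before treatment. Cycles 3 and 4 have no such entry.
- Section 7.13, from Cycle 5 on, has "Additional labs: LDH and TSH (and if TSH is abnormal, then free T3 and free T4). If clinically indicated: ACTH, amylase and lipase".
- Section 7.15, at end of treatment, has "Additional labs: LDH and TSH; and, if TSH is abnormal, then also free T3 and free T4". Section 7.16 has the same set at the 30-day visit and no laboratory tests at the 100-day visit.

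The discretionary list in Section 8.8 reads "ACTH, amylase and lipase done as clinically indicated per judgment of the investigator". It does not name cortisol.

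In Arm A, the Section 7.2 calendar gives "LDH, TSH + reflexive (free T3 & free T4), cortisol, CK, and CK-MB" on Day 1 of all cycles, with troponin-I in a separate, time-limited row. Section 7.8 repeats this for Cycle 2 onward: "cortisol, CK, and CK-MB. If clinically indicated: ACTH, amylase and lipase".

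**The concern.** Ipilimumab is given in Arm B only, as four doses over the first four cycles (Section 9.5). Scheduled cortisol there ends after one of those doses, while Arm A, which receives no ipilimumab, keeps it throughout. The protocol's own background points the other way: hypophysitis is cited more often for nivolumab plus ipilimumab (Section 3.2, Table 1) than for nivolumab plus relatlimab (Section 13.3). Section 11.4 names adrenal insufficiency and ACTH deficiency among the endocrine events to be managed. No reason for the stop is given.

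What is at stake is safety surveillance, not an endpoint. A cortisol that falls without symptoms after Day 22 would have to show itself through TSH, chemistry, examination or later symptoms. A finding could be acted on without ending treatment: Section 11.3 allows treatment to resume when a drug-related endocrine event is controlled with physiologic hormone replacement.

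**Working it through.** The plan states no figure to reproduce here. The check maps doses and draws to nominal study days.

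**Inputs.** Arm B Cycles 1-4 last 21 days, with ipilimumab on Day 1 of each (Sections 7.3 and 9.5). Arm A cycles last 28 days (Section 7.2). Laboratory work on Day 1 of Cycles 2-4 is done before treatment (Section 7.12).

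**Ipilimumab days.** 1 + 21(k - 1) for k = 1 to 4 gives Days 1, 22, 43 and 64. Cycle 5, Day 1 is Day 85.

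**Arm B scheduled cortisol, with ipilimumab doses already given at each draw:**

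| Draw | Study day | Doses already given |
|---|---|---|
| Screening | within 14 days before Day 1 | 0 |
| Cycle 1, Day 1 | 1 | 0 |
| Cycle 1, Day 8 | 8 | 1 |
| Cycle 1, Day 15 | 15 | 1 |
| Cycle 2, Day 1 (pre-dose) | 22 | 1 |
| Cycle 3, Day 1 | 43 | none scheduled (2 doses given) |
| Cycle 4, Day 1 | 64 | none scheduled (3 doses given) |
| Cycle 5, Day 1 | 85 | none scheduled (4 doses given) |

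The last scheduled draw comes 64 - 22 = 42 days before the last ipilimumab dose and 85 - 22 = 63 days before the first visit after it. The allowance for laboratory results up to 3 days old can only move the Cycle 2 draw earlier, so the count of doses is unchanged.

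**Arm A scheduled cortisol.** 1 + 28(k - 1) gives Days 1, 29, 57 and 85, and the draws continue every 4 weeks.

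**Comparison through Day 85.** Arm A has 4 on-treatment draws and Arm B has 4. After Day 22, Arm A has 3 (Days 29, 57 and 85) and Arm B has 0.

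**Cited hypophysitis.**

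- Nivolumab plus ipilimumab, any grade: 202/4,849 = 4.17%, as printed.
- Nivolumab plus ipilimumab, grade 3-4: Table 1 prints a count of 79 and a percentage of 1.53. 79/4,849 = 1.63%, whereas 1.53% corresponds to 74/4,849. Either entry may be the misprint, so the range is about 1.5-1.6%.
- Nivolumab plus relatlimab, grade 3-4: 0.3% (Section 13.3).

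These are pooled rates from different programmes. They support the direction of the difference and no more.

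**The case against.** The schedule is internally consistent, breaks no rule in the protocol and touches no endpoint analysis. Existing cover in Arm B is substantial: every Day 1 visit has examination, weight, vital signs, adverse event review, sodium, potassium, glucose and TSH with reflex free T3 and T4. ACTH may be ordered on clinical indication, and nothing bars an unscheduled cortisol. No Arm B delay or discontinuation rule names cortisol. Steroids are a primary treatment for immune-related events (Appendix 6), and Section 3.2 cites 59% grade 3-4 treatment-related events for this combination, so steroid-suppressed values are foreseeable and could prompt needless work-up. The documents also do not say when hypophysitis arises, or whether cortisol falls before other signs.

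Most of this stands, and it keeps the point small. It does not close the gap: TSH and chemistry do not measure cortisol, and a test ordered on clinical grounds needs a clinical sign first. Steroid interference applies equally in Arm A, where the sponsor still draws cortisol every cycle.

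A reader might infer three stronger things that the documents do not support:

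- That Arm B is sampled less often over the first 12 weeks. It is not; both arms have four draws through Day 85, and Arm B's are front-loaded.
- That a countable number of cases would be missed. Applying 4.17% to 18 patients gives 18 x 202/4,849 = 0.75 expected cases and a chance of 1 - (1 - 0.04166)^18 = 54% of at least one. Those figures are hypophysitis at any time and of any grade, not silent cases in the gap or cases that an added draw would find sooner.
- That events below grade 3 (123/202 = 61% or 128/202 = 63%, depending on which Table 1 entry is right) would be silent. Lower-grade events can have symptoms.

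**Conclusion.** The point holds as one of timing. All of Arm B's scheduled cortisol falls by Day 22, after at most one ipilimumab dose. None follows doses 2, 3 or 4, in the arm whose regimen has the higher cited hypophysitis rate. The calendar and the visit text agree, so this is not an artefact of a broken table.

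The size that can be stated is 0 scheduled draws after Day 22 through Day 85, a span of 63 days, against 3 in Arm A. The clinical yield cannot be computed from the documents, and none is claimed. The day counts assume nominal cycle lengths without delays. Because other monitoring continues every cycle, this is a cheap improvement to safety surveillance, not a defect that threatens the trial.

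**What to change.** In Sections 7.3, 7.12 and 7.13, add cortisol to the Arm B Day 1 draws at Cycles 3, 4 and 5 (Days 43, 64 and 85). These are the pre-dose draws that follow ipilimumab doses 2, 3 and 4. Record current corticosteroid use with each value, so that a steroid-suppressed result is not read as a new adrenal event. If the sponsor prefers the present schedule, give the reason in Section 7.3.

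The cost is three assays per patient on blood already drawn, with no added visit or needle stick: 3 x 18 = 54 assays, or 3 x 20 = 60 if Arm B takes half of the 40 enrolments planned in Section 18.2 (an equal split is assumed). The larger downside is the work-up of low or steroid-suppressed values. The endocrine algorithm in Appendix 6 suggests considering visual field testing, endocrinology consultation and imaging. The number of such work-ups cannot be derived from the documents.

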**On Day 1 of Cycles 2, 3 and 4, the following procedures will be completed in association with Arm B dosing:**

- Pre-Dose Vital Signs ( $\leq 30$  minutes prior to START of nivolumab infusion):
  - Heart rate (HR), blood pressure (BP), and temperature.
- Nivolumab infusion:
  - On Cycles 2-4, Day 1, all patients in Arm B are scheduled to receive nivolumab as a 30 minute ( $\pm 10$  minutes) intravenous infusion.
- Post-Dose Vital Signs ( $\leq 30$  minutes after the END of the nivolumab infusion):
  - Heart rate (HR), blood pressure (BP), and temperature.
- Ipilimumab infusion:
  - On Cycles 2-4, Day 1, all patients in Arm B are scheduled to receive ipilimumab as a 90 minute ( $\pm 10$  minutes) intravenous infusion.
  - Note: Nivolumab and ipilimumab are to be administered as SEPARATE intravenous treatments. On days when both drugs are administered, the nivolumab infusion must be completed BEFORE initiation of intravenous ipilimumab – see [Section 9.7](#).
- Post-Dose Vital Signs ( $\leq 30$  minutes after the END of ipilimumab):
  - Heart rate (HR), blood pressure (BP), and temperature.

### **7.13. Assessments, Arm B: Cycles 5+, Day 1**

**On Cycles 5+, Day 1, the following procedures will be completed prior to protocol-indicated treatment:**

- Physical Exam.
- Weight
- Vital Signs: Heart rate (HR), blood pressure (BP), and temperature.
- ECOG performance status.
- Concomitant medication and Adverse Event review.
- Complete Blood Count (CBC) with differential (including white blood cell count with differential, hemoglobin, hematocrit, and platelet count).
- Blood Chemistry [including sodium, potassium, chloride, bicarbonate or carbon dioxide, blood urea nitrogen (BUN), creatinine, glucose, total bilirubin, AST, ALT, alkaline phosphatase (ALP), calcium, albumin, total protein; magnesium and phosphorus].
- Additional labs: LDH and TSH (and if TSH is abnormal, then free T3 and free T4). If clinically indicated: ACTH, amylase and lipase.
- **On Cycle 5, Day 1:** Peripheral blood sample for correlative research.
- **On Cycle 15, Day 1:** Peripheral blood sample for correlative research.

**On Cycles 5+, Day 1, the following procedures will be completed in association with Arm B dosing:**

- Pre-Dose Vital Signs (≤30 minutes prior to START of nivolumab infusion):
  - Heart rate (HR), blood pressure (BP), and temperature.
- **Nivolumab infusion:**
  - On Cycles 5+, Day 1, all patients in Arm B are scheduled to receive nivolumab as a 30 minute (±10 minutes) intravenous infusion.
- Post-Dose Vital Signs (≤30 minutes after the END of the nivolumab infusion):
  - Heart rate (HR), blood pressure (BP), and temperature.

### **7.14. Imaging Assessments: Every 12 Weeks**

CT/MRI re-scanning:

- Ideally performed every 12 weeks after Cycle 1, Day 1, but for the purpose of scheduling flexibility: Scan completion also permitted with minus 1 to minus 7 day window. The minus 1-7 day scan window is intended for flexibility in scheduling re-scans *between Days 22-28 of Cycles 3, 6, 9, etc of every third cycle in Arm A; between Days 15-21 of Cycle 4 in Arm B; and then between Days 22-28 of Cycles 7, 10, 13, etc of every third cycle in Arm B.*
- Scanning on the same day as Day 1 of a new cycle is discouraged but allowed, provided scan results receive appropriate RECIST review prior to initiating the new cycle of study treatment.
- Evaluation of disease status by CT/MRI including imaging coverage of anatomical

regions as outlined in [Section 8.11](#).

- Additional disease evaluations or increased scan frequency may be performed according to the medical judgment of the patient's study physician, in accordance with the following: In the event of suspected Progressive Disease (PD), a CT/MRI is to be performed as soon as possible. In the event of a Complete or Partial Response (CR/PR), a confirmatory CT/MRI is to be performed no earlier than 28 days after the first assessment of CR/PR.

### **7.15. End-of-Treatment / Withdrawal Assessments**

Reasonable effort should be made to complete End-of-Treatment (EOT) / Withdrawal procedures on the day it is decided that a patient will no longer receive protocol-indicated treatment.

The following EOT procedures must be completed subsequent to and not later than 14 days after study physician decision to permanently discontinue protocol-indicated treatment with nivolumab, relatlimab or ipilimumab (whichever treatment occurs last) and prior to any subsequent anti-cancer therapy:

- Physical Exam.
- Vital Signs: Heart rate (HR), blood pressure (BP), and temperature.
- ECOG Performance Status.
- Weight.
- Concomitant medication and Adverse Event review.
- Complete Blood Count (CBC) with differential (including white blood cell count with differential, hemoglobin, hematocrit, and platelet count).
- Blood Chemistry [including sodium, potassium, chloride, bicarbonate or carbon dioxide, blood urea nitrogen (BUN), creatinine, glucose, total bilirubin, AST, ALT, alkaline phosphatase (ALP), calcium, albumin, total protein; magnesium and phosphorus].
- Additional labs: LDH and TSH; and, if TSH is abnormal, then also free T3 and free T4.
- Serum or urine Pregnancy Test in women of childbearing potential (as defined in [Appendix 4](#)).
- Disease evaluation by CT/MRI (only if the previous CT/MRI was done > 28 days before).
- Biomarker and pharmacodynamic (PD) blood samples.

### **7.16. 30-Day and 100-Day Follow-Up Visit Assessments**

Documented attempt(s) should be made for patient return to the study clinic. It will not be considered a protocol deviation if the patient is physically unable to return for the 30-day and 100-day follow-up visits; such circumstance should be recorded in the study documents, and as much of the follow-up information as possible should be obtained via feasible patient contact and from local and outside facilities.

A follow-up clinic visit is to be completed 30-37 days after patient's final protocol-indicated treatment with nivolumab, relatlimab or ipilimumab (whichever occurs last), in order to undergo the following assessments:

- Physical Exam.

- Vital Signs: Heart rate (HR), blood pressure (BP), and temperature.
- ECOG Performance Status.
- Weight.
- Concomitant medication and Adverse Event review.
- Complete Blood Count (CBC) with differential (including white blood cell count with differential, hemoglobin, hematocrit, and platelet count).
- Blood Chemistry [including sodium, potassium, chloride, bicarbonate or carbon dioxide, blood urea nitrogen (BUN), creatinine, glucose, total bilirubin, AST, ALT, alkaline phosphatase (ALP), calcium, albumin, total protein; magnesium and phosphorus].
- Additional labs: LDH and TSH; and, if TSH is abnormal, then also free T3 and free T4.
- Serum or urine Pregnancy Test in women of childbearing potential (as defined in [Appendix 4](#)).
- Biomarker and pharmacodynamic (PD) blood samples.

A follow-up clinic visit is to be completed 100-114 days after patient's final protocol-indicated treatment with nivolumab, relatlimab or ipilimumab (whichever occurs last), in order to undergo the following assessments:

- Physical Exam.
- Vital Signs: Heart rate (HR), blood pressure (BP), and temperature.
- ECOG Performance Status.
- Weight.
- Adverse Event review.

If a patient discontinues the study for reason other than progressive disease confirmed by CT or MRI (e.g. adverse event), then CT or MRI scans involving sites of known or suspected disease must be continued (if clinically feasible) every 12 weeks ( $\pm$  7 days) for 12 months and then approximately every 24 weeks ( $\pm$  4 weeks) thereafter, relative to date(s) of prior scanning, until disease progression is confirmed by imaging. (Note: If the patient initiates treatment in another clinical trial, then any continuing scans done for this trial may terminate.)

